14	Data management	17
14.1	Confidentiality.....	17
15	Data handling	18
16	Statistical Considerations.....	19
16.1	Sample size calculation	19
16.2	Statistical analysis	20
16.2.1	Summary of baseline data and flow of participants	20
16.2.2	Primary outcome analysis	20
16.2.3	Secondary outcome analysis	20
17	Record keeping and archiving.....	21
18	Study Management Group (SMG).....	21
19	Ethics	21
20	Patient and public involvement (PPI).....	21
21	Monitoring	22
22	Finance.....	22
23	Insurance	22
24	Publication policy	22
25	Intellectual property.....	22
26	References	24
27	Appendix 1 - Schedule of assessments.....	27
28	Appendix 2 – Sample vignette	27

4 List of abbreviations

AE	Adverse Event
APR	Annual Progress Report
CI	Chief Investigator
CONSORT	Consolidated Standards of Reporting Trials
EAPC	European Association for Palliative Care
GSF	Gold Standards Framework
IPR	Intellectual Property Rights
JAS	Judge-Advisor System
LCP	Liverpool Care Pathway
LACDP	Leadership Alliance for the Care of Dying People
MDT	Multidisciplinary Team
NHS R&D	National Health Service Research & Development
OACC	Outcome Assessment and Complexity Collaborative
PaP	Palliative Prognostic Score
PI	Principal Investigator
PiPS	Prognosis in Palliative care Study
PIS	Participant Information Sheet
PPI	Patient and Public Involvement
PPI	Palliative Prognostic Index
PPS	Palliative Performance Scale
REC	Research Ethics Committee
SD	Standard Deviation
SOP	Standard Operating Procedure
SMG	Study Management Group
WOA	Weight Of Advice

5 Study personnel

See protocol cover page for Chief Investigator and Sponsor contact details.

MPhil/PhD Student

[name]

e-mail: [contact]

[contact]

Associate Professor

[name]

e-mail: [contact]

[contact]

Senior Research Fellow

[name]

e-mail: [contact]

[contact]

Research Fellow

[name]

e-mail: [contact]

[contact]

Website Developer

[name]

e-mail: [contact]

[contact]

Statistician/Senior Research Fellow

[name]

e-mail: [contact]

[contact]

Associate Professor

[name]

e-mail: [contact]

tel: [[name]]([contact])

6 Summary

Objective:	To understand in quantitative terms how multidisciplinary teams form intuitive judgements about the prognoses of palliative care patients.
Type of study:	Online psychological experiment.
Study design and methods:	In this study, using the Judge-Advisor System, we will recruit clinicians working in palliative care for adults. Participants will be asked to complete a survey and review five patient summaries ("vignettes") based on real cases derived from a previous study. Clinicians will be presented with key prognostic information and will be asked to provide an estimate of the probability that the patient will survive for two weeks (0-100%). After providing this initial estimate, participants will receive prognostic advice. While in reality all participants will receive the same advice, participants will be randomised into two groups and these groups will be informed that the advice is either: (1) provided by an algorithm; or (2) provided by a team colleague. Participants will then be given the opportunity to give a second, possibly revised estimate in the light of the advice received.
	Study data will be collected using two different recruitment methods (Arm A and Arm B). Participants in arm A will be recruited at a series of (online) seminars, and participants in arm B will be recruited through their hospice employment. All participants will be asked to complete an online questionnaire, including five vignettes. Clinicians will be asked some demographic questions including age, gender, profession and experience.
Study duration per participant:	Approximately 10-15 minutes
Estimated total study duration:	36 months
Planned study sites:	For arm A, we will approach clinicians attending a series of (online) seminars on palliative care. For Arm B, we will approach clinicians working in non-NHS hospices in the UK.
Total number of participants planned:	100-300
Main inclusion/exclusion criteria:	Participants must be clinicians working in palliative care for adults. They must be willing and able to provide informed consent

Statistical methodology and analysis:	
Analysis will be conducted by the study team. Participant demographics will be described.
 
The primary outcome will be the weighting of advice that each judge attributes to the advice that they receive. The weighting of advice reflects the importance that a judge gives to the advice provided and the level to which the judge incorporates this into their decision (ranging from '0' if completely discounting the advice to '1' if shifting completely to the advice). The weighting of advice will be analysed using regression analysis, taking into account the judge's initial and final estimates and the advice given. We will explore whether the weighting of advice is influenced by characteristics of (1) the advisor (a clinician or algorithm); (2) the judge (e.g. seniority); and (3) the advice itself (e.g. distance from judge's initial estimate).

--	--

7 Background and Rationale

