7.4 JAS Research

In traditional JAS research, judges are asked to complete an experimental task that usually requires a quantitative answer. Judges provide an initial estimate and they may also be asked to express a level of confidence regarding the accuracy of this initial decision (Bonaccio and Dalal, 2006). Next, the judge will receive advice, which could come from a real advisor or could be fictional, depending on the aims of the study. The judge is then invited to reconsider the initial estimate and provide a final, possibly revised estimate. Research has focussed on the importance (weighting) that a judge gives to the advice provided and the level to which the judge incorporates this into their decision or not (discounting). When revising estimates, people tend to use two strategies: choosing between two estimates or averaging them. A surprising result of previous research has been that averaging was the more effective strategy across a wide range of commonly encountered environments. Authors have observed that despite this finding, choosing was the preferred strategy although greater accuracy would have been achieved had they always averaged (Soll and Larrick, 2009).

One of the main findings reported in the literature is that people tend to discount advice (Yaniv, 2004b, Yaniv and Kleinberger, 2000b, Bonaccio and Dalal, 2006). Although the appropriate use of advice leads to better judgements (because of the reduction of random error), respondents prefer their own estimates; this is referred to as egocentric discounting (Yaniv and Kleinberger, 2000a). Additionally, the distance of the advice from one's own opinion can affects the weight it receives. High-knowledge respondents discounted the advice given while the low knowledge group averaged less and chose to remain with their own initial judgment more (Yaniv, 2004b).

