4.3 Analysis of the primary objective

In order to assess the level to which participants incorporate the advice into their final estimates of the probability of survival, the WOA is calculated for each participant for each vignette(s). This is done by comparing their final estimate against the initial estimate and the advice provided. The final

estimate of probability of surviving two weeks can be represented as a weighted combination of the participant's initial estimate and the advice received, with the weights being proportional to the extent of the shift towards (away from) the advice. WOA will be defined as $= |f - i|/|a - i|$, where 'i', 'f', and 'a' stand for initial, final, and advice, respectively.

If a participant decides to adhere completely to his or her initial estimate (100% discounting of the advice), the weight of the advice will be 0. If the participant decides to shift completely to the advice then the weight of advice will be 1.0 (0% discounting). Intermediate weights indicate that positive weights were assigned to the initial estimate and the advice (partial discounting).

We will then use multilevel regression analysis accounting for multiple vignettes completed by each participant, to compare the means of the WOA scores for the two arms, the algorithm arm and the clinicians' arm.

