4.4 Analysis of the secondary objective

We will perform regression analyses to explore any associations between participants' weighting policies and characteristics of the participants (profession, gender, age, work environment etc.).

We want to explore any associations between participants' weighting policies and the advice itself (e.g. the strength of the advice) as well. Participants will receive five pieces of advice from the PiPS data. They will receive advice given with high confidence (i.e. the patient has 90% probability of surviving the next 14 days), with lower confidence (i.e. 75% probability of survival) and one where the advice is equivocal (i.e. 50% probability of survival).

Multilevel regression analyses will be used to take into account multiple vignettes are completed by each participant.

5 General statistical considerations

All the statistical summaries and analysis will be performed using Stata version 15 (or above).

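### If distance from the initial estimate is analysed as a predictor of WOA, response noise in an unsigned ratio can create a false negative association; the SAP should specify a model that avoids this

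*Protocol*

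**What the plan says.** Protocol section 6 (statistical methodology) lists three kinds of possible influence on WOA: the advisor, the clinician receiving the advice, and "the advice itself (e.g. distance from judge's initial estimate"). Protocol 7.4 gives the reason for interest in distance: "Additionally, the distance of the advice from one's own opinion can affects the weight it receives".

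The outcome is defined identically in Protocol 16.2.2 and SAP 4.3: "WOA will be defined as $= |f - i|/|a - i|", where i, f and a are the initial estimate, final estimate and advice. SAP 4.3 describes the weights as reflecting "the extent of the shift towards (away from) the advice", but the absolute value drops the direction. The summary describes WOA as "ranging from '0' if completely discounting the advice to '1' if shifting completely to the advice". Neither document gives a rule for a = i, for very small distances, for values above 1, or for movement away from the advice.

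On the advice analysis, SAP 4.4 says: "We want to explore any associations between participants' weighting policies and the advice itself (e.g. the strength of the advice) as well". Its example is strength of advice, illustrated by 90%, 75% and 50% survival probabilities, and Protocol 16.2.3 uses the same example. The model is described only as follows: "Multilevel regression analyses will be used to take into account multiple vignettes are completed by each participant". No distance term or functional form is given.

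**The concern.** The example predictor in the summary, |a - i|, is the denominator of the outcome. Error in the final estimate enters WOA divided by that distance, and the absolute value prevents errors in opposite directions from cancelling. Mean WOA is then too high where the advice lies close to the clinician's own view and roughly right where it lies far away.

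The result would look like a substantive finding: that clinicians discount advice far from their own opinion. The background section already presents distance as affecting weight, so such a result would be readily believed. The secondary objective asks whether integration of advice depends on the advice itself, and Protocol 7.5 says the research is meant to inform clinician training. A reader of the results could not separate the artefact from behaviour.

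**Working it through.** **The plan's own figure.** The documents give none for a distance analysis. The nearest is Protocol Table 1, the width of the 95% interval for the difference between arms. It reproduces: 2 × 1.96 × 0.3 × √(4/200) = 0.166 (stated 0.17) and 2 × 1.96 × 0.4 × √(4/100) = 0.314 (stated 0.31). All 12 entries agree to two decimals, but they do not bear on this point.

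**Step 1: algebra.** Let d = |a - i| and let the true weight w be the same at every distance. Write f = i + w(a - i) + e, with e a response error of mean zero, independent of d. Then

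- signed ratio: (f - i)/(a - i) = w + e/(a - i), which has mean w at every distance;
- WOA as defined: |w + e/(a - i)|, which equals w at every distance if e = 0, but has a mean above w if e can reverse the sign of the shift. This happens most often when d is small.

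The false association therefore needs both response error and the absolute value.

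**Step 2: by hand.** Take w = 0.40 and e normal with SD σ (assumptions). With m = 0.40d, mean WOA = [σ√(2/π) exp(-m²/2σ²) + m(1 - 2Φ(-m/σ))]/d.

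- σ = 5, d = 5: m = 2; (3.68 + 0.62)/5 = 0.86.
- σ = 5, d = 10: m = 4; 5.20/10 = 0.52.
- σ = 5, d = 30: m = 12; (0.224 + 11.803)/30 = 0.40.
- σ = 3, at d = 5, 10 and 30: 0.58, 0.43 and 0.40.

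**Step 3: simulation with no true association.** From the documents: five vignettes per participant; 200 participants, the top of the 100-200 aim; two-sided 5% level. Assumed: advice of 90, 85, 75, 75 and 50; initial estimates centred on the advice with SD 20; mean weight 0.40. Each scenario had 2,000 replicates of a linear regression of WOA on |a - i| with participant-clustered standard errors, dropping a = i.

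| Scenario | Slope per 10 points | Significant at 5% |
|---|---|---|
| Shift exactly proportional, no noise | +0.0002 | 5.4% |
| Weights exactly 0, 0.5 or 1, no noise | -0.0004 | 5.8% |
| Both estimates rounded to nearest 5, no other noise | +0.024 | 72%, none negative |
| Noise in final estimate, SD 2 / 5 / 10 | -0.107 / -0.370 / -0.804 | 100%, all negative |
| SD 5, WOA capped at 1 | -0.10 | 100% |
| SD 5, distances of 10 or less dropped | -0.026 | 56% |
| SD 5, signed ratio | -0.001 | 5.6% |
| Error in recorded initial estimate, SD 5, unsigned | -0.183 | 100% |
| Same, signed ratio | +0.013 | 7.5% |

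**Step 4: other response behaviour.** With whole-number answers and noise SD 3 to 5, the unsigned slope per 10 points was:

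- -0.19 to -0.37 if every answer is noisy;
- -0.08 to -0.15 if 60% of answers exactly keep the estimate or adopt the advice. A run with 40% keeping, 20% adopting and 40% averaging with noise gave -0.066 to -0.136;
- -0.016 to -0.023 if the final estimate never leaves the interval between i and a.

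In the last case the signed and unsigned ratios are identical, so the small residue comes from the bounding and not from the absolute value.

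Without such bounding, a regression of (f - i) on (a - i) and (a - i) × |a - i| gave a distance term within 0.003 per 10 points of the true zero.

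**The case against.** A reader might infer that regressing a ratio on its own denominator must give a negative slope. It does not. Proportional shifts give no slope, and rounding alone gave a small positive one. The fault lies in the absolute value combined with response error.

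A reader might also infer that the plan commits to this regression. Distance is named as a predictor only in a parenthesis of the Protocol summary. The analysis sections give strength of advice as their example, and SAP section 4 calls the analysis mainly descriptive. The summary says the regression takes account of the initial estimate, final estimate and advice, which does not rule out a model of the shift.

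The larger slopes can be challenged too. Protocol 7.4 reports that people prefer choosing between the two estimates to averaging them, and a chooser returns exactly i or a. Noise on every answer implied an SD of WOA per response of 0.66 to 1.12, against the 0.3 to 0.4 expected in Protocol 16.1 (which does not say whether that is per response or per participant mean).

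These limits on mechanism, scope and size stand. They do not remove the point. The examples in SAP 4.4 and Protocol 16.2.3 are open, so distance is not excluded, and the summary's intention has not been withdrawn. An analyst following the SAP would most naturally regress WOA as defined. The false slope remains negative when most answers are exact choices, and it is small only if final estimates stay between i and a, which the documents do not require.

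**Conclusion.** The concern holds in a limited form. If unsigned WOA is regressed on distance, ordinary response noise can produce a false negative association, and the plan has no safeguard. Capping at 1 or dropping distances of 10 points or less reduces the artefact without removing it.

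The plausible size runs from about -0.02 to -0.37 per 10 points at a true weight of 0.40. It depends on the noise SD, the advice values, the spread of initial estimates and the share of exact choices, none of which the documents give. The direction under ordinary noise is well supported; the size is not known.

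This concerns a secondary, exploratory analysis. It would be wrong to infer from it that the randomised comparison of the algorithm and clinician arms is invalid: that comparison does not use distance as a predictor and was not tested here.

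**What to change.** Add one paragraph to SAP 4.4.

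- State whether distance will be analysed. If so, state that unsigned WOA will not be regressed on |a - i|.
- Model (f - i) on (a - i), (a - i) × |a - i| and their interactions with group, with participant random effects. The weight at distance d is the coefficient of (a - i) plus d times the coefficient of (a - i) × |a - i|, and the second coefficient is the distance effect. The model does not divide by distance, so it needs no exclusion for a = i.
- As a sensitivity analysis, use signed WOA, (f - i)/(a - i), with rules stated in advance for a = i and for small denominators. Its variance is large when the advice is close: in the runs made, its SD was 1.1 to 1.9 at distances of 10 or less, against 0.19 to 0.24 above 20.
- When reporting, note that error in the recorded initial estimate enters both the shift and the distance. The signed ratio showed a slight positive bias in that case (+0.013 per 10 points at SD 5).

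The cost is that paragraph and a coefficient slightly less direct to read than WOA. Data collection and study conduct do not change.

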7.1 Background

This study is part of the 'Improving care, assessment, communication and training at end-of-life' (I-CAN-CARE) programme of research. The overall aim of this programme is to improve end-of-life care for patients and their families by better assessment of dying patients, by improved understanding of how clinicians identify dying patients, by improving clinicians' skills in making prognostic decisions and by understanding how prognoses are communicated to relatives of dying patients.

This project uses an experimental design to study decision-making about prognoses within multidisciplinary teams.

7.2 Prognostication

Studies show that patients, carers and clinicians all value accurate prognostic information (Adams et al., 2009, Degner et al., 1997, Kirk et al., 2004, Kutner et al., 1999, Steinhauser et al., 2000, Steinhauser et al., 2001). This information can help patients and family members to make decisions and feel prepared, can help family members to prioritise commitments, and can help to access funding and services, and plan treatment and care in the hospital or community (Pontin and Jordan, 2013).

Clinicians' predictions about length of survival are inaccurate and over-optimistic (Glare et al., 2003, Gwilliam et al., 2013b, White et al., 2016, Christakis and Lamont, 2000) and no clear guidance exists on how clinicians can be taught to perform this task better. Nonetheless, clinical predictions of survival remain the most common method of arriving at a prognostic estimate and the European Association for Palliative Care (EAPC) recommends that the "clinical prediction of survival (in combination with other prognostic factors) is a valid tool to obtain a general prognostic evaluation of patients".

In 2013, due to substantial criticism of the Liverpool Care Pathway (LCP), a care plan that had been designed to help doctors and nurses provide quality end-of-life care, an independent committee

chaired by Baroness Neuberger was asked to review LCP use (Neuberger et al., 2013). A particular concern expressed by many relatives and professionals was that clinician predictions of survival were inaccurate and that this had the potential to adversely affect patient care. A frequent theme of the Neuberger report was that clinicians needed to be better at identifying patients who are dying. The Leadership Alliance for the Care of Dying People (LACDP) responded to the Neuberger review and identified “the recognition of dying” as one of the five key priority areas for improving end-of-life care (Leadership Alliance for the Care of Dying People, 2014, Leadership Alliance for the Care of Dying People). Systematic identification of patients approaching the “end-of-life” was also a key recommendation of the End-of-Life Care Strategy (Department of Health, 2008). The Gold Standards Framework (GSF) service improvement programme (widely used in general practice, nursing homes and increasingly in acute hospitals) uses a needs-based coding system dependent upon whether patients are expected to live for “days”, “weeks”, “months” or “years” (Thomas and Free, 2011). Similarly the Outcome Assessment and Complexity Collaborative (OACC) suite of measures includes a “phase of illness” assessment in which clinicians are asked to judge whether a patient is “stable”, “unstable”, “deteriorating” or “dying” (Witt et al., 2014). However, clinicians’ predictions about length of survival are inaccurate and over-optimistic (Christakis and Lamont, 2000, Glare et al., 2003, Gwilliam et al., 2013a, White et al., 2016) and no clear guidance exists on how clinicians can be taught to perform this task better.

Nonetheless, clinical predictions of survival remain the most common method of arriving at a prognostic estimate and the European Association for Palliative Care (EAPC) recommends that the “clinical prediction of survival (in combination with other prognostic factors) is a valid tool to obtain a general prognostic evaluation of patients (grade A)¹” and that “a second opinion by a more experienced professional could be useful (grade D)²” (Maltoni et al., 2005). This latter recommendation was based on experts’ recommendations (Christakis and Lamont, 2000, Higginson and Costantini, 2002), but more recently a few studies have investigated whether multidisciplinary team discussions can improve the accuracy of prognostic estimates (Gwilliam et al., 2011, Kee et al., 2007). One study investigated whether 6-month survival predictions for patients with newly diagnosed lung cancer made by individual clinicians and the multidisciplinary team (MDT) as a whole became more accurate following MDT discussion (Kee et al., 2007). While clinicians felt more confident following the MDT discussion, this did not lead to better accuracy of individual clinicians, and only slightly better accuracy was found at the group level. Notably, this study did not ask clinicians to explicitly share their prognostic estimates. Our own research has shown that, in patients with advanced cancer, an MDT survival estimate was slightly more accurate than either a doctor’s or a nurse’s estimate alone (Gwilliam et al., 2013a). More broadly, a systematic review has found indications that MDT discussions can lead to significant changes in assessment and management of cancer patients (Pillay et al., 2016). It is thought that a multidisciplinary approach can help to reduce variations and improve

¹ Grade A recommendations relied on research evaluated as level I (impact studies with low risk of bias or homogeneous meta-analyses) or level II (Heterogeneous meta-analyses or confirmatory studies with a low risk of bias)

² Grade D recommendations relied on research evaluated as level V (expert opinion) or inconsistent or inconclusive studies of any level.

consistency of care, provide a learning opportunity for junior staff, and improve communication between different specialties (Ruhstaller et al., 2006).

Another approach to improving accuracy of predictions is to provide advice in the form of a prognostic score. Several scores are available, including the Palliative Prognostic Score (PaP score) (Maltoni et al., 1999, Pirovano et al., 1999), Palliative Prognostic Index (PPI) (Morita et al., 1999), Palliative Performance Scale (PPS) (Anderson et al., 1996) and Prognosis in Palliative care Scales (PiPS)(Gwilliam et al., 2011). One study found indications that doctors' estimates became more accurate when they used the PPI to supplement their own intuitive judgments (Morita et al., 2001). Another recent study showed that, for a cohort of 38 patients, the PaP and the PPI more accurately predicted survival than junior doctors and palliative care experts and the most accurate estimates were obtained when palliative care experts used the PaP score (Tavares et al., 2017).

Qualitative studies have explored how palliative care doctors and nurses formulate a prognostic estimate and how they view this process (Clarkson et al., 2013, Pontin and Jordan, 2013). Clinicians mentioned using objective patient data such as Karnofsky Performance Status as well as less tangible factors such as intuition. One interviewee commented how prioritizing different patient data to formulate a prognosis could lead to disagreements between professionals from different disciplines (Pontin and Jordan, 2013). Furthermore, it was suggested that registered nurses and healthcare assistants working on wards might be best placed to formulate a prognosis, because they spend most time with patients and are closely involved in care delivery (Pontin and Jordan, 2013). While, in practice, many prognostic decisions are taken by a senior doctor, a quantitative study in a multidisciplinary team providing supportive care and palliative radiotherapy for cancer patients has shown that prognoses from doctors were equally (in)accurate as those from other professionals, including nurses, radiation therapists and allied health professionals (Fairchild et al., 2014). It was suggested that nurses, because they spent more time with patients, were therefore better placed to assess certain symptoms and signs. In sum, involving professionals from various disciplines may help to combine knowledge on various symptoms and signs and reduce error. However, the manner in which different estimates are combined to arrive at an MDT estimate is not well understood.

The research team has recently completed a study investigating the accuracy of doctors, nurses and MDT predictions of 14 day survival compared to the accuracy of an algorithm (PiPS2) (Kalpakidou et al., 2018). As part of this study we collected observational data about the clinical condition of 1800+ palliative care patients. Furthermore, the research team has completed another study investigating how individual clinicians decide when a patient is imminently dying by using judgement analysis (Cooksey, 1996, White et al., 2018)

The current study will build on this work by using the Judge-Advisor System (JAS) research methodology to investigate the factors which affect MDT decision-making. The ultimate purpose of this research will be to make recommendations about measures that clinicians can take to improve the accuracy of prognostic judgements. It is recognised that real-world MDT decision-making is inevitably more complicated than our simple experimental set-up will allow. This is one of the reasons why the overall project will also investigate the interactions occurring during MDT meetings using qualitative methods (not described in this protocol). By combining the results from these two different approaches, the project will give a nuanced insight into MDT prognostication.

